10 ADVERSE EXPERIENCE REPORTING AND DOCUMENTATION

10.1 Adverse Events

An adverse event (AE) is any untoward medical occurrence in a clinical investigation of a patient administered a pharmaceutical product and that does not necessarily have a causal relationship with the treatment. An AE is therefore any unfavorable and unintended sign (including an abnormal laboratory finding), symptom or disease temporally associated with the administration of an investigational product, whether or not related to that investigational product. An unexpected AE is one of a type not identified in nature, severity, or frequency in the current Investigator's Brochure or of greater severity or frequency than expected based on the information in the Investigator's Brochure.

The Investigator will probe, via discussion with the participant, for the occurrence of AEs during each participant visit and record the information in the site's source documents. Adverse events will be recorded in the patient CRF. Adverse events will be described by duration (start and stop dates and times), severity, outcome, treatment and relation to study drug, or if unrelated, the cause.

AE Severity

The National Cancer Institute's Common Terminology Criteria for Adverse Events (CTCAE) Version 3.0 should be used to assess and grade AE severity, including laboratory abnormalities judged to be clinically significant. The modified criteria can be found in the study manual. If the experience is not covered in the modified criteria, the guidelines shown in Table 1 below should be used to grade severity. It should be pointed out that the term "severe" is a measure of intensity and that a severe AE is not necessarily serious.

Table 1. AE Severity Grading

Severity (Toxicity Grade)	Description
Mild (1)	Transient or mild discomfort; no limitation in activity; no medical intervention or therapy required. The participant may be aware of the sign or symptom but tolerates it reasonably well.
Moderate (2)	Mild to moderate limitation in activity, no or minimal medical intervention/therapy required.
Severe (3)	Marked limitation in activity, medical intervention/therapy required, hospitalizations possible.
Life-threatening (4)	The participant is at risk of death due to the adverse experience as it occurred. This does not refer to an experience that hypothetically might have caused death if it were more severe.

The specific adverse events that will be solicited include cardiovascular outcomes, using the Division of AIDS (DAIDS) Adverse Events Grading Criteria (<https://rsc.niaid.nih.gov/sites/default/files/daidsgradingcorrectedv21.pdf>).

PARAMETER	GRADE 1 MILD	GRADE 2 MODERATE	GRADE 3 SEVERE	GRADE 4 POTENTIALLY LIFE- THREATENING
Arrhythmia (by ECG or physical examination) Specify type, if applicable	No symptoms AND No intervention indicated	No symptoms AND Non-urgent intervention indicated	Non-life-threatening symptoms AND Non-urgent intervention indicated	Life-threatening arrhythmia OR Urgent intervention indicated
Blood Pressure Abnormalities¹ Hypertension (with the lowest reading taken after repeat testing during a visit) ≥ 18 years of age	140 to < 160 mmHg systolic OR 90 to < 100 mmHg diastolic	≥ 160 to < 180 mmHg systolic OR ≥ 100 to < 110 mmHg diastolic	≥ 180 mmHg systolic OR ≥ 110 mmHg diastolic	Life-threatening consequences in a participant not previously diagnosed with hypertension (e.g., malignant hypertension) OR Hospitalization indicated
< 18 years of age	> 120/80 mmHg	≥ 95 th to < 99 th percentile + 5 mmHg adjusted for age, height, and gender (systolic and/or diastolic)	≥ 99 th percentile + 5 mmHg adjusted for age, height, and gender (systolic and/or diastolic)	Life-threatening consequences in a participant not previously diagnosed with hypertension (e.g., malignant hypertension) OR Hospitalization indicated
Hypotension	No symptoms	Symptoms corrected with oral fluid replacement	Symptoms AND IV fluids indicated	Shock requiring use of vasopressors or mechanical assistance to maintain blood pressure
Cardiac Ischemia or Infarction Report only one	NA	NA	New symptoms with ischemia (stable angina) OR New testing consistent with ischemia	Unstable angina OR Acute myocardial infarction
Heart Failure	No symptoms AND Laboratory or cardiac imaging abnormalities	Symptoms with mild to moderate activity or exertion	Symptoms at rest or with minimal activity or exertion (e.g., hypoxemia) OR Intervention indicated (e.g., vasoactive medications, ventricular assist device, heart transplant)	Life-threatening consequences OR Urgent intervention indicated (e.g., vasoactive medications, ventricular assist device, heart transplant)

PARAMETER	GRADE 1 MILD	GRADE 2 MODERATE	GRADE 3 SEVERE	GRADE 4 POTENTIALLY LIFE- THREATENING
Hemorrhage (with significant acute blood loss)	NA	Symptoms AND No transfusion indicated	Symptoms AND Transfusion of \leq 2 units packed RBCs indicated	Life-threatening hypotension OR Transfusion of $>$ 2 units packed RBCs (for children, packed RBCs $>$ 10 cc/kg) indicated
Prolonged PR Interval or AV Block Report only one > 16 years of age	PR interval 0.21 to $<$ 0.25 seconds	PR interval \geq 0.25 seconds OR Type I 2 nd degree AV block	Type II 2 nd degree AV block OR Ventricular pause \geq 3.0 seconds	Complete AV block
	≤ 16 years of age	1 st degree AV block (PR interval $>$ normal for age and rate)	Type I 2 nd degree AV block	Type II 2 nd degree AV block OR Ventricular pause \geq 3.0 seconds
Prolonged QTc Interval²	0.45 to 0.47 seconds	$>$ 0.47 to 0.50 seconds	$>$ 0.50 seconds OR \geq 0.06 seconds above baseline	Life-threatening consequences (e.g., Torsade de pointes, other associated serious ventricular dysrhythmia)
Thrombosis or Embolism Report only one	NA	Symptoms AND No intervention indicated	Symptoms AND Intervention indicated	Life-threatening embolic event (e.g., pulmonary embolism, thrombus)

AE Relationship to Study Drug

The relationship of an AE to the study drug should be assessed using the following the guidelines in Table 2.

Table 2. AE Relationship to Study Drug

Relationship to Drug	Comment
Definitely	Previously known toxicity of agent; or an event that follows a reasonable temporal sequence from administration of the drug; that follows a known or expected response pattern to the suspected drug; that is confirmed by stopping or reducing the dosage of the drug; and that is not explained by any other reasonable hypothesis.
Probably	An event that follows a reasonable temporal sequence from administration of the drug; that follows a known or expected response pattern to the suspected drug; that is confirmed by stopping or reducing the dosage of the drug; and that is unlikely to be explained by the known characteristics of the participant's clinical state or by other interventions.
Possibly	An event that follows a reasonable temporal sequence from administration of the drug; that follows a known or expected response pattern to that suspected drug; but that could readily have been produced by a number of other factors.

Unrelated	An event that can be determined with certainty to have no relationship to the study drug.
-----------	---

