10.4 Criteria for Discontinuation

Safety will be monitored by the dedicated SMC, led by a qualified Drug and Substance Abuse specialist in the UCSF Department of Medicine (see Section 13 below). The SMC will have full and final authority to stop the study at any point for safety concerns. The decision to proceed with further drug administration will be taken by the Principal Investigator, taking into consideration clinical and laboratory adverse events. The decision to proceed with the next dosing level will be taken by the SMC. Specifically,

dosing will be paused and the SMC will be consulted if one Grade 4 or two Grade 3 drug related adverse events or laboratory abnormalities are reported.

Specifically, safety discontinuation criteria will include:

1. Any serious adverse event assessed as at least possibly related to study treatment:
 - a. Any Grade 4 drug-related adverse event or laboratory abnormality
 - b. Two Grade 3 drug-related adverse event or laboratory abnormality
2. Pregnancy or breastfeeding
3. Requirement for prohibited concomitant medications (see section 7.1)
4. Clinical reasons believed life threatening by the physician, even if not addressed in the toxicity section of the protocol

Study drug-specific hold criteria after the first methamphetamine dose will be based on established protocols adapted from prior stimulant interventional trials (Walsh et. al.

Drug Alcohol Depend. 2010 Jan 1;106(1):28-37. doi: 10.1016/j.drugalcdep.2009.07.011):

- SBP \geq 165 mm Hg or
- DBP \geq 100 mm Hg or
- HR \geq 130 BPM

Resume methamphetamine administration only if values are below the above parameters for at least 3 consecutive minutes.

Stop further methamphetamine administration if the following are reached for 4 minutes or more:

- SBP \geq 180 mm Hg or
- DBP \geq 120 mm Hg or
- HR \geq submaximal HR (i.e., 220 - [age x 0.85])

Such a participant will be observed until cardiac parameters return to normal and will be discontinued from the study.

In addition, any significant ECG abnormality (determined by monitoring medical staff) will suspend further dosing.

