Grade 1 or 2 AEs will not result in any change to the study plans. If there is evidence for a Grade 3 AE that is not caused by the study drug, the study will continue as planned. On the other hand, Grade 3 AEs thought to be possibly caused by the intervention and any Grade 4 AEs will result in a hold on any future enrollments until a decision to proceed or to stop the study is made by the SMC

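### The causality table has no category for a reaction of a type not already known for the drug, so such an event has no defined route into the drug-related Grade 3 count

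*Combined protocol and SAP*

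**What the plan says.** Section 10.1 says that the relationship of an adverse event to study drug "should be assessed using the following the guidelines in Table 2". The table has four rows:

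- *Definitely* opens with "Previously known toxicity of agent; or an event that follows a reasonable temporal sequence from administration of the drug", then adds a known or expected pattern, confirmation on stopping or reducing the drug, and no other reasonable explanation.
- *Probably* needs plausible timing and an event "that follows a known or expected response pattern to the suspected drug; that is confirmed by stopping or reducing the dosage of the drug", and one unlikely to be explained by the participant's condition or other interventions.
- *Possibly* needs plausible timing and an event "that follows a known or expected response pattern to that suspected drug; but that could readily have been produced" through other causes.
- *Unrelated* is "An event that can be determined with certainty to have no relationship to the study drug".

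There is no row for unlikely or not assessable. Section 10.1 also defines an unexpected adverse event, in terms of nature, severity or frequency. New types of event are therefore foreseen.

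Relatedness then drives action. Section 9.1.7 makes dose interruption and discontinuation criteria mandatory only for toxicities attributed to study drug. Section 10.4 pauses dosing and consults the SMC when "one Grade 4 or two Grade 3 drug related adverse events or laboratory abnormalities are reported". The Synopsis (Planned Interim Analyses) uses the same count. Section 13 separately holds future enrolments for "Grade 3 AEs thought to be possibly caused by the intervention" and for any Grade 4 event.

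**The concern.** Sections 9.1.7 and 10.1 require the relation to study drug to be recorded for each adverse event. For a reaction that nobody has yet associated with the drug, the investigator is asked to choose from a list with no valid entry. Well-recognised stimulant effects have a route into the related categories and novel ones have none, although safety review exists partly to detect the novel ones. What is at stake is the dosing pause. If a severe event of a new type is left unclassified, nothing in the protocol says whether it contributes to the two Grade 3 events that trigger the pause.

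**Working it through.** There is no numerical design input to reproduce. The check is to test each category against a defined case and then follow the case through the action rules.

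**Case A: new in nature, plausible timing, cause not settled (for example, a Grade 3 laboratory abnormality of a kind not known for the drug).**

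| Table 2 category | Condition that decides | Fits? |
|---|---|---|
| Definitely | Known toxicity, or known or expected pattern | No |
| Probably | Known or expected pattern | No |
| Possibly | Known or expected pattern | No |
| Unrelated | Certainty of no relationship | No |

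Result: 0 of 4. The *Definitely* row can be parsed in two ways: known toxicity as a stand-alone alternative to everything after it, or as an alternative to the timing condition only. Case A fails under both.

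**Case B: a known effect, but more severe or more frequent than expected.** This too is unexpected under Section 10.1, but it can follow a known pattern, so the related categories remain open. The gap does not extend to it.

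**Case A at Grade 3, Synopsis and Section 10.4.** The count takes drug-related events. Neither place says which Table 2 categories make an event drug related. Section 10.4 lists its Grade 3 and Grade 4 counts under a criterion for serious events at least possibly related. That echoes a Table 2 label but does not cite the table. The event has no defined route in. To show the effect with one known-type drug-related Grade 3 event and one Case A event: the count is 1 + 1 = 2 and the rule fires if Case A is accepted. It is 1 + 0 = 1 and the rule does not fire if Case A is left out. The text does not settle which applies.

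**Case A at Grade 3, Section 13.** The test is whether the team thinks that the event was possibly caused by the intervention. It does not mention Table 2, has no known-pattern condition and states no count of two. Section 13 lets the study continue where there is evidence that the drug was not the cause, which Case A lacks. The event can be caught here. However, the action is a hold on future enrolments. Under Section 8.1 an enrolled participant starts the second treatment phase at Day 77, and an enrolment hold as written does not reach that dose.

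**Case A at Grade 4.** Section 13 holds enrolment regardless of cause. Section 10.4 counts a Grade 4 event only if drug related, although its separate criterion for life-threatening clinical reasons may apply.

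**Secondary point.** *Probably*, and *Definitely* except where known toxicity is read as sufficient alone, need an event "that is confirmed by stopping or reducing the dosage of the drug". With two administrations two hours apart on one day (Section 8.4.1), withholding the second is nearly the only opportunity for this. It does not affect the pausing count, because *Possibly* has no such condition.

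**The case against.** The strongest reply is that the protocol has many safeguards that do not run through Table 2. Section 10.3 requires 48-hour reporting of laboratory values, symptoms and serious events, frequent team review of all reported events, and contact with the study team for any Grade 3 or 4 event. It also gives the SMC authority to stop for any safety concern. Section 10.4 suspends dosing for significant ECG abnormalities and sets blood pressure and heart rate limits with no causality condition. Serious events are reported to the IRB regardless of cause (Section 16.2). Table 2 is called guidelines, and an investigator could read an expected pattern generously, as anything pharmacologically plausible.

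Most of this stands, and it rules out several stronger readings that a reader might infer:

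- *That such events count as zero.* An event that fits no row is unclassified, not *Unrelated*, and Section 10.4 never ties drug related to Table 2. The documents are silent on whether it counts.
- *That the enrolment hold screens these events out.* Section 13 applies its own judgement test and can catch them.
- *That every unexpected event falls through.* Only those unexpected in nature do (Case B above).
- *That relatedness summaries would be biased.* Section 14 plans none, and Section 5.2 names only the incidence and nature of adverse events.

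The reply does not supply the missing category or the missing link to Section 10.4. General review and SMC discretion are not a defined entry into a count that is meant to operate automatically.

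**Conclusion.** The point holds as a gap in definitions. A reaction of a new type, with plausible timing and open causality, fits none of the four categories. It has no defined route into the drug-related Grade 3 count in the Synopsis and Section 10.4, and may be missed there. The Section 13 hold is a partial backstop, because it covers future enrolments and not the dosing of participants already enrolled.

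The practical size is limited: it concerns Grade 3 events of a new type, and drug-related Grade 4 events under Section 10.4, among 10 participants with one dosing day per arm. The documents give no basis for estimating how likely such an event is. The conclusion assumes that the words known or expected carry their ordinary meaning and that investigators apply Table 2 as written. The gap should be corrected because the correction is cheap and improves safety capture. It does not undermine the trial.

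**What to change.** 1. In Table 2, remove the known-or-expected-pattern condition from *Possibly*, so that it covers an event with reasonable timing that other causes could also explain. Alternatively, add a category for plausible but previously unknown reactions.
2. Have the sponsor state how the Table 2 categories map to drug related in the Synopsis and Section 10.4.
3. Reconcile Table 2 with Sections 10.4 and 13. Those two sections also differ on the number of Grade 3 events (two in one, no number in the other), on whether a Grade 4 event must be drug related, and on whether the action applies to dosing or to enrolment. No view is taken here on which pausing rule is right.
4. While the table is open, check whether the condition on stopping or reducing the drug can be applied to a single dosing day.

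The cost is a few lines of text. The downside is that some coincidental events will be classed as possibly related and may prompt an SMC consultation.

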10.2 Serious Adverse Experiences (SAE)

An SAE is defined as any AE occurring at any dose that results in any of the following outcomes:

- death
- a life-threatening adverse experience
- inpatient hospitalization or prolongation of existing hospitalization
- a persistent or significant disability/incapacity
- a congenital anomaly/birth defect

Other important medical events may also be considered an SAE when, based on appropriate medical judgment, they jeopardize the participant or require intervention to prevent one of the outcomes listed.

10.2.1 Serious Adverse Experience Reporting

The study site will document all SAEs that occur (whether or not related to study drug) per [UCSF CHR Guidelines](#). The collection period for all SAEs will begin after informed consent is obtained and end after procedures for the final study visit have been completed.

In accordance with the standard operating procedures and policies of the local Institutional Review Board (IRB), the site investigator will report SAEs to the IRB.

10.3 Monitoring

During the study, safety will be monitored by a Safety Monitoring Committee (SMC), which will be led by a qualified UCSF faculty member in the Department of Medicine with expertise in HIV clinical research (see Section 13 below). The SMC will review all study procedures before the initiation of the study. They will have the full and final authority to stop the study for any safety concern at any point. The Principal Investigator will be the primary medical monitor responsible for study adverse event monitoring and will report adverse events and unanticipated problems to the UCSF IRB and the SMC. All participants will be followed for possible adverse events and unanticipated problems throughout the study period.

Participants will be monitored in an outpatient clinic during the first 6 hours post-dose on dosing days. At each visit, participants will be assessed for any new symptoms, and a study coordinator will obtain vital signs. The study will require 48-hour reporting of all laboratory values, signs/symptoms, and serious adverse events (SAEs). The study will have intensive Phase I safety monitoring, which will include regular and frequent team review (every week for the first 2 months of the study; then every two weeks thereafter) of all reported events. In addition, for any Grade 3 or 4 events, sites will be instructed to contact the study team by email.

- Grade 1 or 2 Toxicity: Participants who develop a Grade 1 or 2 AE or toxicity may continue study treatment. If a participant chooses to discontinue study treatment, the site should notify the study protocol core team as noted above, and encourage the participant to complete any remaining study visits.
- Grade 3 or 4 Toxicity: Participants experiencing Grade 3 or 4 AEs requiring permanent discontinuation of study treatment should be followed closely for resolution of the AE to Grade ≤ 3 and the protocol core team must be notified. Participants discontinuing study treatment should be encouraged to complete any remaining study visits.

[name] will be contacted directly to report medical concerns or questions regarding safety.

[contact]

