	
study single body changes occurring during pregnancy will alter the study results.
 
22. Recent vaccination within the last 2 weeks prior to study baseline visit. Routine or standard of care vaccinations (such as SARS-CoV-2, influenza, pneumococcal, and meningococcal vaccinations) are allowed but must be administered greater than 14 days prior to baseline study visit. For SARS-CoV-2 vaccination, the last dose must be administered at least 14 days prior to baseline study visit.

TEST PRODUCT, DOSE, AND ROUTE OF ADMINISTRATION	
Oral methamphetamine hydrochloride (10 mg, then 15 mg) will be administered in a double-blind fashion and prepared by over-encapsulating commercially available drug with cornstarch.

CONTROL PRODUCT, DOSE AND ROUTE OF ADMINISTRATION	
Placebo capsules will be administered in a double-blind fashion and prepared by over-encapsulating cornstarch.

DURATION OF PARTICIPANT PARTICIPATION AND DURATION OF STUDY	
Participants will be randomized to either of two treatment arms, oral methamphetamine or placebo, using a crossover design with a 31-day washout period in between treatment arms. Participants will be on study for up to 146 days.
 
Screening (for each arm): up to 14 days prior to treatment arm.
 
Treatment (for each arm): 1 day (participants to be admitted to outpatient research unit for a total of 5 hours on the treatment day)
 
Follow-up (for each arm): 31 days after the initial dose for that treatment arm.
 
The total duration of the study is expected to be 146 days (approximately 5 months).

CONCOMMITANT MEDICATIONS	
Prohibited:
 
Strict criteria for potential medications that could interact with the study drug will be used, and the following medications are not allowed during the study because of potential interactions with the study medication: acebropyline, iobenguane, isocarboxazid, methylene blue, moclobemide, phenylzine, procarbazine, rasagiline, safinamide, selegiline, tranylcypromine, asunaprevir, bupropion, topical cocaine, fluoxetine, iohexol, linezolid, paroxetine, potassium citrate, quinidine, sodium bicarbonate, sodium citrate, sodium lactate, tipranavir, and tromethamine. This is because the study medication may alter metabolism of the drugs.
 
Allowed:
 
Otherwise, participants may use their usual medications, as long as they are medically necessary and can be monitored safely during the study period.

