8.4 Supply of Study Drug at the Site

8.4.1 Dosage/Dosage Regimen

An initial 10 mg of oral methamphetamine study drug will be administered to assess tolerability, followed by a subsequent 15 mg oral dose two hours later. For placebo treatment phase, one placebo capsule will be administered orally on treatment day, followed by a second oral placebo capsule two hours later.

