8.7 Measures of Treatment Compliance

Study participants will be monitored in the Clinical Research Services Center (CRS) for directly observed therapy on the day(s) when study drug or placebo administered. They will be receiving clinical and laboratory assessments on those days for up to 4 hours post-treatment.

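### The 5-hour treatment-day stay in the synopsis cannot hold the 6 hours of post-dose monitoring required by section 10.3, and the dose that starts the clock is not named

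*Combined protocol and SAP*

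**What the plan says.** Four places in the combined protocol and SAP bear on the length of the treatment day.

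- **Synopsis, duration of participation.** Treatment is one day per arm, with "participants to be admitted to outpatient research unit for a total of 5 hours on the treatment day". This is a total stay and has no dose clock.
- **Section 8.7, Measures of Treatment Compliance.** Dosing in both phases is directly observed at the Clinical Research Services Center. On the assessments made there, the section says: "They will be receiving clinical and laboratory assessments on those days for up to 4 hours post-treatment".
- **Section 10.3, Monitoring.** "Participants will be monitored in an outpatient clinic during the first 6 hours post-dose on dosing days".
- **Section 8.4.1, Dosage Regimen.** The first methamphetamine dose is "followed by a subsequent 15 mg oral dose two hours later". Placebo is likewise given as two administrations with the same interval between them.

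Sections 8.7 and 10.3 do not say whether their windows run from the first or the second administration. The Study Events Table, to which sections 8.1 and 9 refer, is a separate document and was not available for this review.

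**The concern.** The synopsis limits the time in the unit, and section 10.3 sets a period of safety monitoring that is longer than that limit. A coordinator who books the unit from the synopsis would therefore plan a day that cannot meet section 10.3, in either period of the crossover.

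What is at stake is the completeness of safety observation late in the treatment day. The hours at risk come after the second administration, which in the methamphetamine period is the larger of the two doses (15 mg after 10 mg). Cardiovascular events are specifically solicited in this trial (section 10.1), and only 10 participants are planned. If some participants leave at 5 hours and others stay longer, adverse events in the later hours will not have been looked for equally.

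**Working it through.** This is timeline arithmetic; no power or error-rate calculation is involved.

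**Inputs**

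- Total stay: S = 5 h (synopsis).
- Time from first to second dose: g = 2 h (section 8.4.1, both phases).
- Monitoring window: 6 h, reference dose not stated (section 10.3).
- Assessment window: at most 4 h, reference dose not stated (section 8.7).
- Time in the unit before the first dose: p. No value was found, so it is kept as p ≥ 0. Taking p = 0 is the case most favourable to the plan.

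**Step 1. What a 5-hour stay gives**

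- After the first dose: S − p = 5 − p, so at most 5 h.
- After the second dose: S − p − g = 5 − p − 2 = 3 − p, so at most 3 h.

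Both are maxima. Pre-dose procedures reduce them. Section 10.4 also allows the second dose to be held, and a delay of d hours leaves 3 − p − d after it.

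**Step 2. What each window needs**

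With the clock from the first dose, the stay needed is p + window. With the clock from the second dose, it is p + 2 + window.

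| Window | Clock from | Stay needed | Compared with 5 h |
|---|---|---|---|
| 6 h (10.3) | first dose | 6 + p | short by 1 + p |
| 6 h (10.3) | second dose | 2 + 6 + p = 8 + p | short by 3 + p |
| 4 h (8.7), used in full | first dose | 4 + p | fits if p ≤ 1 h |
| 4 h (8.7), used in full | second dose | 2 + 4 + p = 6 + p | short by 1 + p |

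**Step 3. Can any choice of clock make the figures agree?**

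The 6-hour window does not fit the 5-hour stay under either clock, even with p = 0. The 4-hour figure is an upper limit, so fewer hours also comply: the 3 hours available after the second dose satisfy it, and all 4 hours from the first dose fit if p ≤ 1 h. Sections 8.7 and 10.3 share an end point if the 4 hours run from the second dose (2 + 4 = 6) and the 6 hours from the first (0 + 6 = 6). That end point is still 1 hour beyond the stay when p = 0. The conflict that cannot be removed is therefore between the synopsis and section 10.3.

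**Step 4. Could monitoring continue somewhere else?**

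The synopsis speaks of an outpatient research unit, section 8.7 of the Clinical Research Services Center, and section 10.3 of an outpatient clinic. No transfer between locations is described, so the different names do not account for the missing time.

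**The case against.** The best case against the point is that it is narrower than it first looks. Four stronger readings are tempting, and the documents do not support them.

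1. **That three windows contradict one another.** Section 8.7 sets an upper limit on clinical and laboratory assessments, under a compliance heading. Assessments may end before safety monitoring does, and the limit can be respected within 5 hours. This objection stands: only the missing reference dose remains for section 8.7.
2. **That the hold and stop rules in section 10.4 fail.** Those rules apply after the first methamphetamine dose and decide whether the one remaining dose is given. That decision normally falls about two hours in, or somewhat later after a hold, and so inside the 5-hour stay. A participant who meets the stop thresholds is also kept under observation until cardiac parameters are normal, with no fixed hour limit. This stands as well. The possible loss therefore concerns participants who do not meet those thresholds.
3. **That samples and vital signs would be taken at inconsistent times.** Within-day times may be fixed in the Study Events Table, which was not available, and nothing in the text ties sampling to the length of stay. This effect is not shown. The table could settle sampling times, but the synopsis and section 10.3 would still disagree.
4. **That methamphetamine and placebo days are observed for different lengths of time.** The synopsis states the stay for each arm, section 10.3 covers dosing days generally, and the dose spacing is the same in both phases. Nothing in the plan makes the window depend on treatment.

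It could also be said that staff would simply keep participants for the longer time. They might, but the plan does not tell them to, so early discharge is a possibility and not a prediction. None of this reconciles a 5-hour total with 6 hours post-dose.

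**Conclusion.** The point holds as an internal inconsistency between the synopsis and section 10.3. The 5-hour stay is at least 1 hour short of the required monitoring counted from the first dose, and at least 3 hours short counted from the second. These shortfalls assume that the first dose is given on arrival and the second exactly two hours later; pre-dose time increases both, and a delayed second dose increases the second.

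The consequence is modest but practical. On either treatment day, adverse events after the second dose could be seen less completely in participants who do not meet the section 10.4 stop thresholds. The dose-hold decisions, the sampling times and the balance between treatments are not shown to be affected. The documents do not establish which of the two durations was intended, and this review takes no position on that.

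**What to change.** Reconcile the synopsis, section 8.7 and section 10.3. For each of the two windows, state the administration from which it is counted. Then make the stated stay in the unit consistent with the stated monitoring window, allowing for the two-hour dose interval and any pre-dose procedures. If monitoring is meant to continue in a different location after the unit stay, say so. Check the Study Events Table against the agreed text. The length of the window is for the investigators to decide.

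The cost is a change of wording and possibly a longer clinic booking on two days per participant.
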